3.1.2 Secondary Objectives

- 2. Does the fixed Twinblock appliance produce more skeletal than dentoalveolar contribution for a Class II division 1 malocclusion in comparison to the conventional removable Clark Twinblock appliance?
- 3. Does the fixed Twinblock appliance produce more facial volume increase in comparison to the conventional removable Clark Twinblock appliance?
- 4. Are patient's treatment experience better with the fixed Twinblock appliance as compared to the removable Twinblock appliance.
- 5. Is the fixed Twinblock appliance more cost effective and safer for correcting increased overjets as compared to the removable Twinblock appliances.

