3.2.2 Secondary Outcomes

- 2. Relative skeletal, facial and dentoalveolar contributions to overjet correction by comparing lateral cephalogram changes via cephalometric analyses (Mills 1982), and facial volumetric changes (Camison et al 2018) and tooth movements by superimposing 3D scans, respectively, at the end of orthodontic treatment.
- 3. Patients' perception and experience with the fixed and removable Twinblock appliance will be assessed using the three questionnaires approach (Pre-Treatment questionnaire, Orthodontic Experience Questionnaire and Post-Treatment questionnaire (Al-Naseri et al 2017)
- 4. Cost-effectiveness of overjet reduction with fixed and removable Twinblock by comparing direct costs of treatment i.e., number of visits for Twinblock phase of treatment and number of breakages/loss with the fixed and removable Twinblock appliances.
- 5. Potential adverse effects of the fixed Twinblock and removable Clark Twinblock appliance.

Table 1: Primary Objectives and Outcome Measures

Primary Objective:	Outcome Measure:	Timepoint of outcome measured
Rate of Overjet correction	change in millimetre/month from clinical measurements	T0, T1, T2, T3, T4, T5

Table 2: Secondary Objectives and Outcome Measures

Secondary Objective:	Outcome Measure:	Timepoint of outcome measured
Skeletal, facial and dentoalveolar contributions to overjet correction	Lateral cephalometric analyses, Facial volumetric changes, and tooth movements by superimposing 3D scans	T0, T4, T5
Patients' perception and experience	Pre-Treatment questionnaire, Orthodontic Experience Questionnaire and Post- Treatment questionnaire	T0, T1, T4
Cost-effectiveness of treatment	Number of visits for Twinblock phase of treatment and number of breakages/loss	Τ4

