Vectra® H1 handheld 3D camera will be used to record the patient's three-dimensional (3D) facial characteristics, allowing quantification of 3D soft tissue volume changes. The camera works like any other and would require three facial captures which are automatically stitched into one 3D image with the provided software. The whole process will take 10 minutes. The need for 3D quantification of the soft-tissue effects of functional appliances has been highlighted (Flores-Mir 2006). The immediate soft tissue effects, especially of the soft tissue chin (Sharma 2005) have been shown to be only 40% of the predicted outcome (Salloum 2018). Landmarking of the pre- and post-treatment 3D images will be done using the VAM (Vectra Analysis Module) software and superimposed to measure the difference in linear distance in millimetres.

Lateral Cephalogram

Cephalometric radiographs are routinely taken as part of assessment and planning for orthodontic treatment. Modern digital lateral cephalometric radiographs are very low dose. It is used to assess whether the aetiology of malocclusion is due to skeletal relationship, dental relationship or both and quantify treatment changes. The radiographs will be taken at baseline, end of twinblock treatment and towards end (near end) of fixed appliance treatment in accordance with normal clinical practice. Eastman cephalometric analysis (Mills, 1982) will be done on the radiographs to assess the skeletal and dental changes associated with both the groups. The analysis will include angles SNA (sells-nasion-point A), SNB (sella-nasion-point B), ANB (difference between SNA and SNB), upper incisor long axis to maxillary plane (anterior nasal spine -posterior nasal spine), lower incisor to mandibular plane (gonion-menton), MMPA (maxillary-mandibular plane) and linear measurements - facial proportion (ratio of lower face height to total anterior face height) and APog (tip of lower incisor form line connecting point A-Pogonion)

Patient Experience questionnaire

This validated questionnaire, based on the three-questionnaire approach, will evaluate patients perception of their malocclusion pretreatment (T0) and patients' experience with wearing the fixed and removable Twinblock appliances 3 months into treatment (T1) and at the end of Twinblock phase of treatment (T4).

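### Section 6.1 takes only a linear landmark distance from the 3D facial images, but secondary objective 3 asks about facial volume; for objective 2, the listed sagittal skeletal measures are angles only

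*Protocol*

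**What the plan says.** **Objectives (section 3.1.2).** Objective 2 asks: "Does the fixed Twinblock appliance produce more skeletal than dentoalveolar contribution for a Class II division 1 malocclusion", against the removable appliance. Objective 3 asks: "Does the fixed Twinblock appliance produce more facial volume increase in comparison to the conventional removable Clark Twinblock appliance".

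**Outcome (section 3.2.2 and Table 2).** Outcome 2 serves both objectives. It is defined as "Relative skeletal, facial and dentoalveolar contributions to overjet correction by comparing lateral cephalogram changes via cephalometric analyses", together with facial volumetric changes and "tooth movements by superimposing 3D scans, respectively, at the end of orthodontic treatment". Table 2 repeats facial volumetric changes as an outcome measure and gives the timepoints T0, T4 and T5.

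**Measurements (section 6.1).**
- 3D facial images: the text says the camera makes it possible to quantify soft-tissue volume. The measurement then described is landmarking of the pre- and post-treatment images, which are "superimposed to measure the difference in linear distance in millimetres".
- Lateral cephalogram: "The analysis will include angles SNA (sells-nasion-point A), SNB (sella-nasion-point B), ANB (difference between SNA and SNB". The list continues with upper and lower incisor inclination, the maxillary-mandibular plane angle, a face-height ratio, and the distance of the lower incisor tip from the A-Pogonion line.
- Intraoral scans: landmark distances in mm between superimposed scans, named as the source for the dental contribution to overjet reduction.
- Overjet: mm, by ruler.

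**Analysis (section 8.2).** Secondary measures are explored with descriptive statistics.

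**The concern.** A secondary objective is answered only if the quantity measured is the quantity asked about. For the face, the question, the outcome and the outcome table all say volume, while the measurement text says distance. A site or image analyst who follows section 6.1 will produce a table of landmark shifts, and the report will have no volume to set against objective 3.

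For objective 2 the difficulty is one of units. Overjet is a sagittal distance in mm, and a relative contribution to its correction is a share of that distance. The dental side is planned in mm, from the scans. The skeletal side is planned in degrees. Without a skeletal component in mm, the two sides cannot be put on one scale directly.

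**Working it through.** The protocol gives no figure for objectives 2 or 3, so the check is mainly one of dimension.

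**1. Objective 3: required against specified.**

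| Place | Quantity |
|---|---|
| Objective 3 (3.1.2) | facial volume |
| Outcome 2 (3.2.2) | facial volumetric change |
| Table 2 | facial volumetric change |
| Camera capability (6.1) | volume change can be quantified |
| Measurement described (6.1) | linear distance, mm |

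A volume difference is an integral over the region between two surfaces (mm³). A landmark distance is the separation of two points (mm). Distances at a few landmarks do not determine the volume between them: the same landmark shift can go with different changes in the surface around it. Section 6.1 gives no facial region, volume unit or volume computation. The mismatch is therefore confirmed for the specified measure. It does not extend to the images themselves.

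**2. Objective 2: the eight listed cephalometric measures by type.**

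| Type | Measures | Count |
|---|---|---|
| Angle, sagittal skeletal | SNA, SNB, ANB | 3 |
| Angle, skeletal, vertical | maxillary-mandibular plane angle | 1 |
| Angle, dental | upper and lower incisor inclination | 2 |
| Ratio | face-height proportion | 1 |
| Distance in mm, dental | lower incisor tip to A-Pogonion | 1 |

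Total 3 + 1 + 2 + 1 + 1 = 8. Skeletal displacements in mm: 0.

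**3. What a partition of overjet change needs.** Measure forward displacement along one reference line. Let a and b be the displacements of an upper-jaw and a lower-jaw point, and u and l those of the upper and lower incisor tips, all in mm. Then

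overjet reduction = l − u = (b − a) + [(l − b) − (u − a)].

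The first term is skeletal and the bracket is dental, and they sum exactly. The listed angles supply neither a nor b. Converting a change in SNA or SNB to mm would need a length from nasion to the jaw point for each child, and no such length is listed.

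**4. Can the scans fill the gap?** In principle the skeletal part could be taken as a remainder: overjet change minus dental movement. The protocol does not say so. The scan measure is described only as a distance between landmarks, without a sagittal axis or sign. If the three components of a landmark's movement are x (sagittal), y and z, the distance is √(x² + y² + z²), which is at least |x| and carries no direction. It need not equal the sagittal movement that enters the overjet sum.

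**5. Is anything else affected?** The sample size rests on a difference of 81 days with SD 101. A two-sided independent t-test (sidedness is not stated, so two-sided is assumed) at alpha 0.05 and 80% power gives 25.4, rounded up to 26 per arm, as planned. With 40% loss, 26 / 0.6 = 43.3, rounded up to 44 per arm and 88 in total, also as planned. None of these inputs involves objectives 2 or 3.

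**The case against.** **The data will support volume.** Table 2 and outcome 2 name volumetric change, and section 6.1 says the camera permits it. This stands: the fault is in one sentence describing the measure, and nothing irrecoverable is lost. A reader might infer that the trial will be unable to answer objective 3 at all. The documents do not support that, because the images needed are scheduled at T0, T4 and T5.

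**Objective 2 does not rest on the radiographs alone.** Outcome 2 also uses tooth movements in mm, which section 6.1 names as the dental source. The cephalometric list is introduced as what the analysis will include, so it need not be complete. Skeletal and dental angles can still be compared between arms. This also stands, and it defeats the stronger inference that the planned measures cannot answer objective 2. What remains is that no skeletal quantity in mm is stated. A rule for combining components may properly sit in the SAP, and its absence here is not the point; such a rule would still need a skeletal input on the same scale.

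**Timing.** The outcome 2 text, read alone, suggests comparison only after the fixed-brace phase common to both arms. Table 2, however, lists T4, section 4.5 explains why T5 is added, and section 14.2 plans publication of data analysed at the end of Twinblock treatment. Only the wording needs aligning.

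**The 1–2 mm skeletal growth in section 2.** A reader might treat this as a benchmark that the planned output must match. It is background literature, and the protocol sets it nowhere as a target.

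**Conclusion.** The point holds in a limited form. For objective 3 there is an internal inconsistency: three places require volume, and the only measurement described is a linear distance. As written, the specified measure does not answer that objective. For objective 2 the point is secondary: all three listed sagittal skeletal measures are angles, none of the eight listed measures is a skeletal displacement in mm, and the angles cannot be combined directly with the scan distances into shares of overjet change. Between-arm comparison of the angles remains possible and informative.

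One of the four secondary objectives lacks a matching measure, and a second has one only in part. Both are analysed descriptively, so the primary analysis and the sample size are untouched. The conclusion assumes that section 6.1 will be followed as written, and that the protocol is right that its camera system can quantify volume.

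**What to change.** 1. **Section 6.1, stereophotogrammetry.** Specify as the measure for objective 3 the soft-tissue volume difference between the superimposed T0 and follow-up 3D surfaces, over a defined facial region and with its unit. Keep landmark distances as supportive. Alternatively, restate objective 3, outcome 2 and Table 2 as landmark displacement.
2. **Section 6.1, lateral cephalogram.** Add the sagittal mm displacement of an upper-jaw point, a lower-jaw point and both incisor tips along one common reference line. Skeletal and dental parts then sum to the overjet change measured on the radiograph and can be reported in mm and as shares by arm. Keep the listed angles.
3. **Section 3.2.2, outcome 2.** Align the stated time of comparison with the T0, T4 and T5 of Table 2.

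The images and radiographs are already scheduled, so no further visit or exposure is needed. The cost is processing of the 3D surfaces, some extra tracing time and a protocol amendment.

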6.2 DATA MANAGEMENT SYSTEM

Data management will be conducted in compliance with TASC SOPs on Data Management, TASC SOP53 Data Management Systems in Clinical Research and TASC SOP48 Data Management in CTIMPs using Excel.

The data management system (DMS) will be Excel, as approved by Sponsor.

The DMS will be based on the protocol and CRF for the trial and individual requirements of the investigators. The CRF will collect only information that is required to meet the aims of the trial and to ensure the eligibility and safety of the participant. The trial database will be compliant with TASC SOP53 Data Management Systems in Clinical Research.

The database is managed in line with all applicable principles of medical confidentiality and UK law on data protection, namely, the General Data Protection Regulation. The Data Controller will be the University of Dundee and the Data Custodian will be Chief Investigator.

The CI may delegate CRF completion but is responsible for completeness, plausibility and consistency of the CRF. Any queries will be resolved by the CI or delegated member of the trial team.

Database lock will be conducted in compliance with TASC SOP32 Locking Clinical Study Databases.

7 CLINICAL PROTOCOL AND TRIAL PLAN

7.1 FIXED TWINBLOCK APPLIANCE DESIGN

The fixed Twinblock (*Figure 1*) comes as preformed occlusal blocks and wires. The occlusal blocks will be custom adapted to the individual participant's models with the upper block fitted to cover the second premolar and extend distally over the molars. The lower block will cover the premolars, avoiding the cusp of the canine.

In occlusion, the occlusal blocks will be inclined at 70° to allow forward positioning of the lower jaw. The fixed Twinblocks will be cemented onto the occlusal surfaces simply with conventional glass ionomer cement. The upper palatal arm can be expanded (prior to cementation) to allow for upper arch expansion.

Figure 1: Fixed Twinblocks with occlusal blocks adapted to the teeth and supporting wire components.

7.2 REMOVABLE TWINBLOCK APPLIANCE DESIGN

The removable Twinblock (*Figure 2 & 3*) design used in this trial will be upper and lower appliances with clasps on upper 1st premolars and 1st molars, lower 1st premolars and lower incisors for retention. Where additional retention is deemed to be required clinically, clasps will be included on lower molars, in addition to above. The upper appliance will include a jack screw for expansion and no labial bow will be used.

In occlusion, the occlusal blocks will be inclined at 70° to allow forward positioning of the lower jaw.

Figure 2 & 3: Removable Twinblocks with jack screw in the upper arch and clasps for retention

7.3 TRIAL PLAN

Gantt Chart (Table 3) with details of the clinical trial

Tasks	Jul- Dec'20	Jan- June'21	Jul- Dec'21	Jan- June'22	Jul- Dec'22	Jan- June'23	Jul- Dec'23	Jan- June'24
Ethical approval								
Setting up RCT								
Recruitment								
Data Collection								
Data analysis								

8 STATISTICS AND DATA ANALYSIS

8.1 SAMPLE SIZE CALCULATION

The feasibility study conducted by us in Dundee Dental Hospital (REC 17/ES/0126) has produced a clear route of progression (NIHR criteria) to the substantive multicentre RCT by estimating all the important parameters. Using initial data obtained from our feasibility study, for an effect size of 0.80 (difference of 81 days and SD 101 days), an alpha value of .05 and a power of 80% the required sample size was computed as 26 participants per group giving a total of 52. This is a assuming a simple independent t-test analysis and utilising sample size software PASS20. Recruitment will be across 4 sites and so randomisation will be stratified by site. With the long nature of treatment and high levels of drop out, combined with missing data from non-treatment visits we decided to allow for 40% drop out or incomplete data collection and therefore 88 patients will be recruited, 44 to each arm of the trial.

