There are a variety of options for prominent upper front teeth in adolescents. The bite blocks (Twinblocks) invented by William Clark are a two-piece removable brace and these are frequently used in treatment. They work by harnessing the muscular forces to move the teeth and the jaws. Due to the growth potential in younger patients, response of the jaws to treatment can be greater and, in many cases, substantial prominence of upper front teeth can be fully corrected. Patients who wear the removable bite blocks on a full-time basis in the presence of active growth inevitably show an excellent treatment result, whilst those that fail to wear these, fail to produce any positive changes. The issue with compliance has been quantified by Parekh et al (2019) for the Twinblock appliance at mean daily wear of 12.38 hours or 51.6% of that recommended. The solution to the problem of compliance is to develop a fixed bite block appliance that is effective. The compliance, comfort and speed of treatment with fixed bite block brace treatment remains to be tested.

Hence in this clinical trial, we propose to compare the effects of the fixed and removable bite blocks (Twinblocks) in correcting upper prominent front teeth in 120 growing individuals aged between 09 to 14 years old. The speed of correction, changes to the teeth, jaws and face, cost effectiveness and psychosocial aspects of treatment will be studied amongst participants from Tayside and Grampians regions within Orthodontic specialist practices and Hospital services.

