3.2 OUTCOMES

3.2.1 Primary Outcomes

1. Rate of overjet correction by comparing change in millimetre/month from clinical measurements with fixed and removable Twinblock appliances.

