4.9 NUMBER OF PARTICIPANTS

We plan to undertake a multicentre randomised clinical trial in Tayside (primary and secondary care) and Grampian (primary care) regions as a two-arm parallel design of fixed and removable Twinblock appliance for overjet reduction. To detect a clinical important difference, 26 participants per arm, giving a total of 52 are required to complete the trial. With the long nature of treatment and high levels of drop out, combined with missing data from non-treatment visits, it was decided to allow for 40% drop out or incomplete data collection and therefore 88 patients will be recruited, 44 to each arm of the trial. The recruitment is anticipated to take around 18-months to complete.

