8.2 PROPOSED ANALYSES

Descriptive statistics will be prepared to show the mean, standard deviation and range for the outcome variables in the fixed and removable Twinblock groups.

The primary outcome measure will be millimetre change in overjet per month. This will be compared between the fixed Twinblock group and the removable Twinblock control group using a Multilevel Linear Model (MLM). This will allow us to assess the difference between treatment groups while controlling for any differences in effect between treatment centres. In the event that the collected data violates the assumptions for a parametric test, heterogeneity between centres will be assessed using the MLM and checked with a Friedman's ANOVA within treatment groups. If no heterogeneity between returning centres is observed, data from all centres will be collapsed and a bootstrapped independent t-test will be run. If both non-parametric data and heterogeneity between centres and a Bonferroni correction will be applied for running multiple analyses. Estimates of effect size will be calculated from the data to better inform the sample size calculations of future studies.

The effect of the Twinblock appliance upon secondary measures will be explored using descriptive statistics. Data on the patients' perceptions and experience of their appliances will be analysed with descriptive statistics to produce graphs and tables

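### The 80% power is calculated for a difference in days, but the primary outcome is overjet change in mm/month, and no target difference or SD is given on that scale

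*Protocol*

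**What the plan says.** Section 8.1 bases the sample size on the sponsor's feasibility study. It is calculated "for an effect size of 0.80 (difference of 81 days and SD 101 days". With alpha at 0.05 and 80% power, this yields 26 completers in each arm, 52 in all, and the calculation is described as "assuming a simple independent t-test analysis and utilising sample size software PASS20". The section then decides to "allow for 40% drop out or incomplete data collection and therefore 88 patients will be recruited, 44 to each arm of the trial". Section 4.9 repeats the result: "To detect a clinical important difference, 26 participants per arm, giving a total of 52 are required to complete the trial".

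The primary outcome is on another scale. Section 3.2.1 reads "Rate of overjet correction by comparing change in millimetre/month from clinical measurements", and Table 1 gives the same measure at T0 to T5. Section 8.2 reads "The primary outcome measure will be millimetre change in overjet per month" and analyses it with a multilevel linear model that allows for treatment centre. No primary or secondary outcome in section 3.2 is a duration in days. Nowhere does the protocol give a difference, SD or effect size in mm/month, or convert days into mm/month.

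Separately, the Introduction describes the comparison as being made "in 120 growing individuals aged between 09 to 14 years old", while the Summary and sections 4.9 and 8.1 all say 88.

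**The concern.** Power belongs to a particular variable and a particular analysis. A standardised difference of 0.80 in days does not become 0.80 in mm/month. A rate depends on the millimetres corrected as well as on the time taken. The millimetres will differ between patients, because entry is open to any overjet of 6 mm or more, randomisation is stratified by two overjet grades, and the Twinblock phase aims at 0 to 3 mm. Dividing by time also changes the shape and spread of the distribution.

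Two things are at stake. The power statement is the stated justification for recruiting 88 children, and it has not been shown to apply to the endpoint on which the trial will be judged. Also, if the result is null, there is no pre-stated mm/month difference against which to read the confidence interval, although section 4.9 says that the size was chosen to detect an important one.

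**Working it through.** **1. The plan's own figure (inputs from section 8.1).** Difference 81 days, SD 101 days, alpha 0.05, power 80%, independent t-test.

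- Standardised difference: d = 81/101 = 0.802.
- Normal approximation: n per arm = 2(1.960 + 0.842)²/d² = 15.70/0.643 = 24.4, so 25.
- Exact (noncentral t, two-sided): n = 25.4 for d = 0.802 and 25.5 for d = 0.80, so 26 per arm. Power at 26 is 80.9% and 80.7% respectively.
- Section 8.1 does not say whether alpha is one- or two-sided. Two-sided reproduces 26; one-sided gives about 20.
- Dropout: 26/(1 − 0.40) = 43.3, so 44 per arm and 88 in total.

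The stated figures all reproduce, for a variable measured in days.

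**2. What the size implies on the primary scale.** With 26 completers per arm and a two-sided t-test, power depends on the unknown standardised difference in mm/month:

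| d in mm/month (assumed) | Power, 26 per arm |
|---|---|
| 0.5 | 42% |
| 0.6 | 56% |
| 0.7 | 70% |
| 0.8 | 81% |
| 0.9 | 89% |

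The protocol does not allow a choice between these rows.

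**3. Why 81 days does not fix the row.** The following inputs are assumptions. The removable mean is 274 days, borrowed from the nine-month literature average in section 2, so the fixed mean is 274 − 81 = 193 days. The mean correction is 7 mm, a figure that the protocol does not give. Rate = change/time, with 30.44 days per month.

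- At the mean times: 7/(274/30.44) = 0.78 and 7/(193/30.44) = 1.10 mm/month, a difference of 0.33 before rounding.
- Averaging each patient's rate, with lognormal times and every patient corrected by exactly 7 mm: means 0.88 and 1.41, SDs 0.33 and 0.74. The difference is 0.53, the pooled SD is √((0.33² + 0.74²)/2) = 0.57, and d is about 0.92.

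The same 81 days therefore corresponds to different mm/month differences, according to the distribution of times and how the rate is formed.

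**4. Illustrative power on mm/month** (simulation, 26 per arm, unadjusted t-test, removable mean 274 days, mean correction 7 mm with SD 0 to 2 mm):

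| Distribution of times | Difference and SD in days | Power on mm/month |
|---|---|---|
| Gamma | 81 and 101, held | about 75% to 87% |
| Lognormal | 81 and 101, held | about 83% to 95% |
| Normal, gamma or lognormal, limited to 60–365 days | changed to about 69–73 and 79–86 | about 57% to 95% |

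In each of the first two rows, the low end is at SD 2 mm and the high end at SD 0. The third row must be read apart from the others, because limiting the times alters the planning inputs. For normal times the ratio in days stays at 69/86 = 0.80; for lognormal times it rises to 73/79 = 0.92. Wider assumptions widen the range: lognormal times held at 81 and 101 days, with a removable mean of 330 days and a correction SD of 7 × 0.40 = 2.8 mm, give about 57%.

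**The case against.** Days and mm/month both describe the speed of correction, which is the trial's stated aim, so a sponsor may reasonably plan on one and report the other. Section 8.1 is also open about its simplification to a t-test. The illustration rests on arm means and a correction that the protocol does not give. It tests only one construction of the rate: a slope fitted to the serial readings at T0 to T5 need not behave like total change over total time, and allowing for baseline overjet could recover some power. The estimate and confidence interval in mm/month will be valid whatever scale was used for planning.

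Most of this stands, and it limits the conclusion. It does not supply the missing mm/month difference and SD. Nor can the gap be left to an analysis plan, because the protocol gives a complete justification of size on a scale that its own primary outcome does not use.

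Some stronger readings are not supported:

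- A reader might infer that the trial is underpowered. The illustrative range lies on both sides of 80%, so this is not shown.
- A reader might take 57% as the power under the planned 81 and 101 days. In the 274-day illustration that figure appears only after the times are limited, which changes those inputs. Elsewhere it needs a different assumed mean and a wider spread of correction.
- A reader might call this an arithmetic error. Every stated figure reproduces.
- A reader might blame the multilevel model. With individual randomisation stratified by site, adjusting for centre need not lower power.
- A reader might say that 81 days is time to correction. Section 8.1 says only days, so that is an inference.

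**Conclusion.** The concern holds as a mismatch between the endpoint used for planning and the primary endpoint. The sample size is correct for a difference of 81 days with SD 101 days. It does not establish 80% power, or a clinically important difference, for overjet change in mm/month. This conclusion rests on the text alone and needs none of the simulation assumptions.

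The size of the effect on power cannot be fixed from the protocol. On the assumptions in the working, with 81 and 101 days held, the illustration gives about 75% to 95% across gamma and lognormal times. Other plausible assumptions go lower. True power could be above or below the stated 80%.

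The 120 in the Introduction is a clerical slip with no bearing on this point.

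**What to change.** From the overjet readings of the feasibility study, state in section 8.1 the expected difference and SD in mm/month, with the rate formed as the primary analysis will form it. Section 2 reports overjet reduction at 3 months from the study with the same ethics reference, so the sponsor should already hold millimetre data.

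Then restate, in sections 8.1 and 4.9, the power for 52 completers on the planned primary analysis, and say that alpha is two-sided if that is intended. If the sponsor prefers, give the detectable difference instead: for a plain t-test at 26 per arm and 80% power this is about 0.80 × the SD in mm/month. Section 4.9 should say why that difference matters clinically, or drop the claim that it does.

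Keep 88 recruited. Separately, change 120 to 88 in the Introduction.

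Making days the primary endpoint in order to keep the 81-day figure is not a sound shortcut. Section 6.1 limits the Twinblock phase to 12 months and requires the overjet to be unchanged at two consecutive appointments. Patients not corrected by then would be censored, and the t-test power would still not apply.

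The cost is one recalculation on existing data and a wording amendment. The restated power may be less favourable than 80%, and the protocol should then say so.
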